We will first perform analyses to test and quantify the extent to which the effect of the decision aid intervention on patient engagement endpoints is mediated through the mitigation of candidate preparatory and interactional barriers. We will quantify the indirect effect relative to the total effect of the decision aid in joint linear structural equation models (SEM) for the endpoint and the candidate mediators, including random surgeon effects and random region effects for each of the mediator and endpoint parts of the models. Each of the preparatory and interactional Barriers will be represented by a continuous latent construct in the SEM, with 3 and 5 observed items for Preparatory and Interactional Barriers, respectively. Binary or count variables will be modeled via latent continuous construct in the SEM. Structural equation models will be specified, estimated and tested using Mplus v7.3.⁹⁷ The use of unidimensional latent constructs increases power and reduces the number of tests, relative to testing each observed item separately. Standardized coefficient estimates from the SEM, representing total, direct, and indirect effects, will allow for the determination of whether the mechanism by which the decision aid leads to increased patient engagement is through the mitigation of preparatory and/or interactional barriers (see Figure 7 for simplified example). For example, if coefficient X is important but Y is not, we can conclude that although the decision aid leads to statistically significant changes in interactional barriers, this is not the mechanism through which the decision aid increases patient engagement. Alternatively, if only coefficient Y is important, we can conclude that although the interactional factors represent a significant barrier to patient engagement, the decision aid does not significantly impact the barrier.

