12.1.2 Sample Size and Power Calculations

Co-Primary Objective #1: Based on current patient enrollment, we estimate a sample size of 563 patients. This has been reduced from our original estimate of 1,050 patients. We assume 23 surgeons will participate. Aim 1 has two primary endpoints: PEPI-5 self-efficacy and Active Patient Participation Behaviors (count). We desire a family-wise two-sided Type I error rate of $\alpha=0.05$; under a Bonferroni correction, tests will be conducted with nominal of $\alpha=0.05/2 = 0.025$.

Using the revised analysis model and updated accrual projections, we estimated Fisher's information for the regression parameters when the study will have complete data; inverting that information we obtained an estimate of the standard error for the intervention effect parameter, thereby computing minimally detectable Cohen's-*D* effect size for each primary endpoint at 80% and at 90% power. As a sensitivity analysis, we considered varying estimates of ICCs to ensure robust findings.

Self-Efficacy: Assuming PEPI-5 has a standard deviation (SD) of 4.3 and both within-surgeon and within-site-between surgeon ICC of 0.07, we will have 80% power to detect effects as small as $0.55*4.3=2.4$ and 90% power to detect effects as small as $0.63*4.3=2.7$ on a scale of 5-25. We consider a difference of 2 points to be clinically meaningful.

Active Patient Participation Behaviors: Assuming the active patient participation behavior count has a standard deviation of 23.1 and a within-surgeon ICC of 0.01 and within-site-between surgeon ICC of 0.0001, we have 80% power to detect a difference of $0.50*23.1=11.6$ and 90% power to detect a difference as small as $0.57*23.1=13.2$ on a 0-150 scale. We consider a difference of 10 to be clinically meaningful.

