Co-Primary Objective #2: Mackinnon *et al.* have shown that one of the most accurate tests for mediation or indirect effect is the “asymmetric distribution of products” test¹⁰⁰ and have provided extensive simulation studies for estimating power for a variety of mediation tests.^{101,102} PowMedR software¹⁰³ was developed based on that work, which we exploit here. We assume a sample size of 563 and then deduct 23 df for surgeon effects and 7 df for number of waves; we estimate an effective sample size of 533. In addition, because we are testing two mediators, we set $\alpha=0.05/2 = 0.025$ for these two tests. Suppose we have small mediation effects with $R^2=2\%$ for the effect of the intervention on the *latent* barrier mediator (Figure 7) and for the effect of the latent mediator on PEPPi-5 score or on active patient participation behavior count. Suppose additionally that the three observed items have correlation of at least $r=0.60$. Then, the average of those three items will have reliability of $\lambda = \{r + (1/3)(1 - r)\}$, yielding net R^2 values between the intervention and the *observed* mediator and between the observed mediator and PEPPi-5 score or active patient participation behavior count of $\lambda R^2=0.82*.02=1.6\%$. Using the PowMedR software, we will have 60% power to detect mediation with small effect size and >99% power to detect mediation with medium effect size $\lambda R^2=0.82*.15=12.3\%$. Power will be higher with five items.

We will extend the period of enrollment for sites that are still recruiting within the stepped wedge design as of 8/30/2021. The extended recruitment beyond Wave 7 will continue for six sites until 12/31/2021 (see Section 12.1.3). While these additional patients will not contribute to the first co-primary objective, they will be included in the analysis for this 2nd co-primary objective; all of these additional patients will be exposed to the study intervention. We anticipate, at a minimum, that there will be 50 such patients exposed to the intervention across these six sites. We re-estimated power assuming such an increase, which leads to an increase in the power for detecting small effects from 60% to 65%.

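### Should the mediation alpha be split over four tests (two mediators on two endpoints) instead of two?

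*Combined protocol and SAP*

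**What the plan says.** Section 12.1.2, Co-Primary Objective #2, divides the 5% by the number of mediators: "In addition, because we are testing two mediators, we set" alpha at 0.05/2 = 0.025 "for these two tests". The mediators are the latent preparatory and interactional barriers. The power scenario assumes a small effect of the intervention on the barrier and the same size "for the effect of the latent mediator on PEPPi-5 score or on active patient participation behavior count". The method it cites is the "asymmetric distribution of products" test.

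Section 12.1.1 sets out to quantify how far the "effect of the decision aid intervention on patient engagement endpoints is mediated through the mitigation of candidate preparatory and interactional barriers". It then describes joint structural equation models for the endpoint, in the singular, and the candidate mediators. The null hypothesis is that the product of X (aid to barrier) and Y (barrier to engagement) is zero.

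Two neighbouring paragraphs of 12.1.2 name their families. For Objective #1: "We desire a family-wise two-sided Type I error rate of" 0.05, halved over PEPPI-5 and the participation count. For the socioeconomic-disadvantage tests there is a family-wise 0.05 over up to four barriers. The mediation paragraph names no family, and no section selects, orders or pools the two endpoints for mediation.

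**The concern.** Two mediators and two endpoints make four tests, but the alpha is divided by two. Objective #1 protects 5% across these same two endpoints, so a reader may expect the same for mediation, which section 2.1 lists as co-primary. If the 5% were meant to cover all four tests, 0.025 each would not hold it.

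The configuration that causes trouble is one the plan raises itself: section 12.1.1 discusses what to conclude "if coefficient X is important but Y is not". If the aid moves both barriers and neither influences engagement, each of the four tests can give a false positive at close to its nominal level. One significant result in four could then be reported as the mechanism of the decision aid, under a 5% label that was never defined for the set.

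**Working it through.** **Inputs from section 12.1.2.** Alpha 0.025 per test, taken as two-sided as elsewhere in that section. Effective sample size 563 - 23 - 7 = 533, or 583 with 50 further patients. Small effect R² = 0.82 × 0.02 = 0.0164 per path; medium effect R² = 0.82 × 0.15 = 0.123. Stated small-effect power 60% and 65%.

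**1. The plan's own power.** Path noncentrality is sqrt(n R²/(1 - R²)).
- n = 533: sqrt(533 × 0.0164/0.9836) = 2.98. n = 583: 3.12. Medium effect, n = 533: 8.65.
- The critical value at two-sided 0.025 is 2.241. Requiring both paths to be significant gives Phi(2.98 - 2.241)² = 0.770² = 59% at n = 533, and 0.810² = 66% at n = 583.

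This matches the stated 60% and 65%, so the stated power was computed for a single test at 0.025.

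**2. Error within one endpoint (two tests).** The ceiling is 2 × 0.025 = 5%. With both barriers moved, Y null and independent tests, a small first path gives 1 - (1 - 0.770 × 0.025)² = 3.8%. A strong first path gives 1 - 0.975² = 4.9%. Simulation over a range of correlations never exceeded 5%.

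**3. Error over both endpoints (four tests).** The ceiling is 4 × 0.025 = 10%. With both barriers moved, Y null and independence:
- Small first path: 0.770 × (1 - 0.975²) = 0.0380 per mediator, then 1 - (1 - 0.0380)² = 7.5%.
- Strong first path: 1 - 0.975⁴ = 9.6%.

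Simulation with mediator correlation 0-0.4 and endpoint correlation 0-0.8 (assumed; the documents give neither):

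| Truth | Medium paths | Small, n = 533, joint significance | Small, n = 533, product test |
|---|---|---|---|
| Both barriers moved, Y null | 7.5-9.6% | 5.9-7.5% | 5.0-6.3% |
| One moved with Y null; other not moved but Y real | 6.4-7.4% | 5.2-6.0% | 4.4-5.3% |

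At n = 583 the small-effect first row is 6.2-7.9% by joint significance and 5.3-6.8% by the product test. The other patterns stay at about 5% or less by joint significance: one barrier moved with Y null while the other truly mediates (3.1-5.0%) or has both paths null (3.1-5.1%), and neither barrier moved (4.0-5.0%). With every path null the error is about 0.2%.

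**4. Precision of the first path.** Step 3 uses n = 533 as if patients were independent. The detectable effects for Objective #1 come from the stepped-wedge model: 0.50 to 0.55 SD at 80% power and alpha 0.025. They imply a standard error of 0.50/(2.241 + 0.842) = 0.16 to 0.55/3.083 = 0.18 SD. With equal arms (assumed), R² = 0.0164 is d = 2 × sqrt(0.0164/0.9836) = 0.26, so the noncentrality is about 1.45 to 1.6, not 2.98. With both barriers moved and Y null, the four-test error is then 1.7-2.5% by joint significance and 1.1-1.7% by the product test. For the medium effect the noncentrality is 4.2 to 4.6 and the error remains 7.1-9.6%. This step assumes that barriers are measured about as precisely as the endpoints and that the mediator equation carries the same time terms.

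**5. Price of controlling all four.**
- Bonferroni at 0.05/4 = 0.0125 (critical value 2.498): small-effect power is Phi(2.98 - 2.498)² = 47% at n = 533 and 54% at n = 583.
- Holm: the same 47% and 54% if one effect is real, rising to 55-56% and 62-64% if all four are.
- Fixed endpoint order with a separate gate for each mediator: 60%/65% kept on the first endpoint. On the second, 46-53% (n = 533) or 53-60% (n = 583) if the same mediator acts on both endpoints, and 2% or less if it acts on the second only.

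Medium-effect power stays above 99% at both 0.025 and 0.0125.

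**The case for a change.** The strongest case for a change is consistency. The paragraphs on either side of the mediation calculation name their family and divide by the full number of tests. This one does not, although it serves a co-primary objective and mentions both endpoints. An unstated family can be chosen after the results are seen, and one added sentence would prevent that.

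The omission is real, and so is the arithmetic: with medium effects on both barriers and no effect of either on engagement, the four-test error is well above 5% even at stepped-wedge precision. But the family-wise statement for Objective #1 is made for that objective's tests and is not extended to mediation. The explanation given for 0.025, two mediators and therefore two tests, fits a separate model for each endpoint without strain. The objection shows that a sentence is missing, not that a stated error rate is breached. Choosing the stricter family instead would cost power that is already modest. A fixed order would also require ranking two endpoints to which the plan gives equal alpha.

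**Conclusion.** No change is needed. Within each endpoint, 0.025 for two mediators holds 5%, and this is the natural reading of the analysis model. An analyst would report the two indirect effects endpoint by endpoint, and a reader can see that there are two such reports.

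If 5% over all four tests were wanted, the excess would be confined to particular truths: up to 9.6% in the simulations with medium effects, 5.0-7.5% with small effects at n = 533 (up to 7.9% at n = 583), and about 2% with small effects at stepped-wedge precision. These figures rest on the assumed correlations and, for the last, on the assumptions in step 4. Removing the excess would take small-effect power from about 59% to 47% at n = 533 when one effect is real, or leave almost none for an effect confined to the second endpoint. For an analysis of mechanism, that is a trade-off on which reasonable statisticians differ.

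The downstream effect is also limited. Section 12.1.1 carries barriers forward on coefficient Y alone as well as on the indirect effect, and the disadvantage tests that follow have their own 5% family.

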10.1.4.2 Interactional Barriers

- Power Imbalance

Surgeon Facilitative Behaviors (audio-recording of consult): In addition to assessing active patient participation, the validated system developed by Street, et al., also measures the degree to which physicians used partnership-building and supportive talk.^{65,75,76}

Health Care Climate Questionnaire (follow-up patient survey): The Health Care Climate Questionnaire (HCCQ) is a validated patient survey that was developed to assess patient's perceptions of the degree to which their specific doctor is autonomy supportive. It consists of 15 items. We will use this instrument to assess Patient Self Autonomy and Trust in Provider.

- Clinicians' Interpersonal Characteristics

Surgeon recommendation (audio-recording of consult): We will collect whether the surgeon provided a recommendation, and when in the consultation this occurred. We will classify this as early recommendation versus late/no recommendation based on whether it occurs in the first quarter of the consultation.

Family member presence (audio-recording of consult): We will observe if a family member is present during the visit with the surgeon.

Practitioner Orientation Scale (surgeon baseline survey): The Practitioner Orientation Scale measures the roles that doctors believe they should play in the course of their interaction with patients. The total score for this 18-item scale, ranging from patient-centered to doctor-centered, can be calculated in addition to two sub-scores. The first nine-item sub-scale, Sharing, reflects the extent to which

the respondent believes that patients desire information and should be part of the decision making process. The second nine-item sub-scale, Caring, reflects the extent to which the respondent sees the patient's expectations, feelings, and life circumstances as critical elements in the treatment process.⁸⁰

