Finally, if we find significant indirect effects (represented in the figure by the dashed line leading from the decision aid to engagement that runs through interactional barriers), we can conclude that receipt of the decision aid leads to a change in the interactional barrier, which leads to improved patient engagement. Statistically, coefficients X and Y will be tested together, with the null hypothesis being that the product $XY=0$. If either latent construct for preparatory or interactional Barriers is significant, then each individual observed item will be tested, post hoc, as candidate barriers. Candidate barriers for the next models will be barriers for which the indirect effect is significant and/or barriers associated with lower levels of engagement (i.e. coefficient Y). Those barriers associated with lower level of engagement will be considered persistent and prioritized for inclusion in the qualitative interviews (Aim 3).

Persistent Barriers Experienced by Socioeconomically Disadvantaged Patients

We will estimate logistic and Poisson regression models with socioeconomic deprivation as the explanatory variable, and each candidate persistent barrier as described above as the outcomes, in order to assess the extent to which socioeconomic disadvantage is associated with persistent barriers to engagement. As with Aim 1, models will include surgeon and clinic random effects to account for patient clustering. Findings will guide the sampling strategy for patient interviews (Aim 3) and will be incorporated into the interview content.

[figure not shown]

Figure 7. Schematic depicting the mediating role of preparatory and interactional barriers on engagement. The dashed lines represent the test for the overall effect of whether the decision aid improves engagement through that pathway.

*Effect of decision aid on barriers; +Effect of barriers on patient engagement.

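### The interactional barriers include a surgeon score fixed before enrollment, which the patient-level mediation and disadvantage models cannot use; the claim of higher power with five items is unsupported

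*Combined protocol and SAP*

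**What the plan says.** For Co-Primary Objective #2, section 12.1.1 represents each barrier domain by a continuous latent construct in a structural equation model, "with 3 and 5 observed items for Preparatory and Interactional Barriers, respectively". Surgeon random effects enter both the mediator and the endpoint parts. If either construct is significant, each observed item is tested post hoc as a candidate barrier. Barriers that show an indirect effect or an association with engagement then go into regressions on socioeconomic disadvantage, with "each candidate persistent barrier as described above as the outcomes" and with surgeon and clinic random effects.

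Section 10.1.4.2 lists five interactional measures: surgeon facilitative behaviors, the Health Care Climate Questionnaire (HCCQ), timing of the surgeon's recommendation, family member presence, and "Practitioner Orientation Scale (surgeon baseline survey): The Practitioner Orientation Scale measures the roles that doctors believe they should play". Sections 7.2.1 and 10.1.6 place the surgeon survey before patient enrollment and data collection, and it is given once.

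Section 12.1.2 assumes a correlation of at least 0.60 among three items, reaches a reliability of 0.82 and 60% power for small effects (65% with 50 more patients), and then states "Power will be higher with five items".

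**The concern.** A score recorded once per surgeon before the trial starts cannot do what the plan asks of a mediator item. It precedes the intervention, and it is identical for all of a surgeon's patients. If it is one of the five items, one of the interactional barriers in a co-primary objective cannot be estimated or tested as specified. The power sentence is also affected. More items raise reliability only if they correlate well enough, and a surgeon-constant score can correlate only weakly with measures that vary mainly between patients. The reader is led to expect more than 60% power for the interactional pathway with nothing shown to support it.

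**Working it through.** **Structural check (no ICC needed).**

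- Path X (decision aid to barrier): the score is fixed before any clinic crosses over, so its true path X is zero, and so is its indirect effect XY. Any observed association with exposure reflects only which surgeons contributed patients to which period.
- Latent factor: with surgeon random effects in the mediator part, a patient-level factor is identified from variation within surgeon. This score has none.
- Disadvantage model: as an outcome with a surgeon random effect, the score is reproduced exactly by that effect. No residual variation is left for a patient's disadvantage to explain.

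**Inputs for power (section 12.1.2).** The plan will "deduct 23 df for surgeon effects and 7 df for number of waves" from 563, so 563 − 23 − 7 = 533 ("we estimate an effective sample size of 533"). Alpha: "because we are testing two mediators, we set $\alpha=0.05/2 = 0.025$ for these two tests". R² = 0.02 for each path on the latent scale; r = 0.60 for three items.

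**Reproducing the plan's figure.** Three-item reliability is 3(0.60)/(1 + 2×0.60) = 0.818, the 0.82 that the plan uses. (The formula as printed gives 0.733, perhaps a term lost in text extraction.) Observed R² = 0.82×0.02 = 0.0164. Power is the product of the two path powers, each from a two-sided noncentral t test with noncentrality √(N·R²/(1−R²)).

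- N = 533: noncentrality √(533×0.0164/0.9836) = 2.98, critical value 2.248, power per path 0.768; 0.768² = 59.0% (stated 60%).
- N = 583: power 65.2% (stated 65%).

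**Ceiling for the surgeon score.** Its correlation ρ with a patient-level item is at most the square root of that item's between-surgeon share of variance. The plan gives no ICC for any barrier, so the endpoint ICCs are borrowed as an assumption: 0.01 (participation count), 0.07 (PEPPI-5), and 0.14 if the two PEPPI-5 components add. The ceilings are 0.10, 0.265 and 0.374. A correlation of 0.60 would need an ICC of 0.36.

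**Five-item average.** Let four items correlate at r with each other and the fifth at ρ with each of them. The squared correlation of the average with the factor is (4√r + ρ/√r)² / (5 + 12r + 8ρ). This is generous to the fifth item, because it credits a fixed score with a share of path X.

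| Case (N = 533) | Reliability | Power |
|---|---|---|
| Three items, r = 0.60 | 0.82 | 59.0% |
| Four at 0.60 + score, ρ = 0.10 | 3.2275²/13.0 = 0.801 | 57.4% |
| Four at 0.60 + score, ρ = 0.265 | 3.440²/14.32 = 0.827 | 59.6% |
| Four at 0.60 + score, ρ = 0.374 | 3.581²/15.19 = 0.844 | 61.1% |
| Four alone, r = 0.60 | 2.4/2.8 = 0.857 | 62.1% |
| All five at 0.60 | 3.0/3.4 = 0.882 | 64.2% |
| Four alone, r = 0.40 | 1.6/2.2 = 0.727 | 50.6% |
| Four alone, r = 0.30 | 1.2/1.9 = 0.632 | 41.2% |

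Four items match three items at 0.60 when r = 0.818/(4 − 3×0.818) = 0.529. The plan names the distribution-of-products test. A simulation of that test gives 55.8% for three items and 59.0% for four at 0.60, so the ordering is the same.

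**The case against.** The strongest objection is that the five items are not identified. Section 12.1.1 gives counts only, and counting measures fails for the sister construct: section 10.1.4.1 lists four preparatory measures against three items. The HCCQ is said to cover both autonomy and trust; counted as two, the interactional list has six entries and Practitioner Orientation might not be among the five. This stands, so the match is an inference. It is also a reason to name the items. Whatever the composition of the factor, section 10.1.4.2 classes the scale as an interactional barrier.

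A reader might infer that the plan assumes 0.60 for all five items, that this is impossible, and that five items therefore lower power. The documents do not support that. The 0.60 is stated only for three items. The impossibility is strict only within surgeon. Several interactional measures describe the surgeon's own behavior, so their between-surgeon share may exceed the endpoint ICCs. The second figure in "within-surgeon ICC of 0.01 and within-site-between surgeon ICC of 0.0001" concerns patients of different surgeons at one site and does not set the ceiling. The planned model is also a latent construct rather than an average: an uninformative item could take a near-zero loading, leaving four items and 62%, above the three-item figure.

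Finally, the disadvantage-model problem arises only if the scale passes the earlier screen, and the power sentence drives no sample size. Both points stand and limit the consequence.

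**Conclusion.** The structural defect holds for any model in which the scale is used as a patient-level barrier: zero path X by design, no within-surgeon variance, and no residual variance as an outcome with surgeon random effects. Its place among the five items is inferred from the list in section 10.1.4.2.

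The five-item sentence is unsupported rather than shown to be false. With four items at r = 0.60, power is about 57-61% with the score averaged in at its ceiling and 62% without it, against 59% for three items. That is a change of about −2 to +3 points, resting on assumed surgeon ICCs of 0.01-0.14. The larger uncertainty is the correlation among the other four. Two are yes/no variables and the sources mix audio and survey, so values below 0.53 are plausible; at 0.30-0.40, four-item power is about 41-51%. That loss would come from those four items, not from the surgeon score. The plan's 60% and 65% for three items are reproduced and stand.

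**What to change.** 1. Name the observed items of each construct in section 12.1.1, including whether the HCCQ counts once or twice.
2. Take Practitioner Orientation out of the interactional latent factor, the post hoc item mediation tests and the disadvantage outcome models. Use it only as a surgeon-level predictor of engagement.
3. Replace the five-item sentence with power for the four remaining items over a stated range of correlations, for example r = 0.3 to 0.6 (about 41% to 62% by the calculation above).

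The cost is SAP wording and one recalculation, with no new data. The restated power will probably look less favourable, and the surgeon-level effect will be imprecise because it rests on 23 surgeons.

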Once mediating barriers are detected, we use a model similar to that in Aim 1 to test for an association of each barrier to a baseline indicator of socioeconomic disadvantage. We assume 30% of the sample will be disadvantaged, evenly distributed among clinics and surgeons. Assume we will be testing up to four barriers; as we desire a family-wise two-sided Type I error rate of $\alpha=0.05$, under a Bonferroni correction, tests will be conducted with nominal of $\alpha=0.05/4 = 0.0125$. Extending the same method of computing power as in Aim 1, we will have power of 80% for an effect size of 0.31 and 90% power to detect an effect size of 0.35.

We then re-estimated power assuming an additional 50 intervention patients enrolled beyond Wave 7 across six sites. As a result, the study will have 80% power to detect an effect size of 0.30 and 90% for an effect size of 0.34.

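### The disadvantage tests use 0.05/4 per barrier, but the selection rule sets no limit of four, so the desired 5% family-wise error holds only if four or fewer barriers are carried forward

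*Combined protocol and SAP*

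**What the plan says.** Section 12.1.2 (Co-Primary Objective #2) describes tests of whether each barrier is associated with socioeconomic disadvantage. It states: "Assume we will be testing up to four barriers"; "as we desire a family-wise two-sided Type I error rate of" 0.05; and "under a Bonferroni correction, tests will be conducted with nominal of" 0.05/4 = 0.0125. For these tests "We assume 30% of the sample will be disadvantaged, evenly distributed among clinics and surgeons". The resulting claim is that "we will have power of 80% for an effect size of 0.31 and 90% power to detect an effect size of 0.35". With at least 50 extension patients, "the study will have 80% power to detect an effect size of 0.30 and 90% for an effect size of 0.34".

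Section 12.1.1 settles which barriers reach those tests. The structural equation model has two latent constructs, "with 3 and 5 observed items for Preparatory and Interactional Barriers, respectively". If either construct is significant, "each individual observed item will be tested, post hoc, as candidate barriers". A barrier goes forward if its indirect effect is significant, or if it is associated with lower engagement, or both. Each barrier that goes forward becomes the outcome of a logistic or Poisson model with disadvantage as the explanatory variable. Section 12.1.1 gives no alpha for these models, no maximum number and no ranking.

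**The concern.** The divisor of four is an assumption made in the power section. The number of tests is set by a rule in the analysis section that can admit any number up to the full item count. The two are not linked. If the plan is followed as written and more than four barriers qualify, each is still tested at 0.0125 and the 5% family-wise rate is no longer assured.

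More than four is possible. A barrier can qualify through its association with engagement alone, there are two engagement endpoints, and Section 12.1.2 itself assumes that items within a construct are substantially correlated, so related items would tend to qualify together.

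Whether persistent barriers fall disproportionately on disadvantaged patients is part of a co-primary objective (Section 2.1). The answer also steers interview sampling and content. A false positive would point later work on adjunct interventions at the wrong barrier.

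**Working it through.** **Inputs.** Family-wise alpha 0.05 two-sided, divisor 4 and 30% disadvantaged come from Section 12.1.2. The sample is n = 563, or 563 + 50 = 613 with the extension. The item count is 3 + 5 = 8 (Section 12.1.1).

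**Step 1: reproduce the plan's figures at four tests.** I treat the effect size as a standardised mean difference. I apply no design effect, because disadvantage is assumed evenly spread within clinics and surgeons.

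Detectable effect = (z for 1 − α/2 + z for power) × √(1/n₁ + 1/n₂), with n₁ = 0.3n and n₂ = 0.7n.

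- α = 0.05/4 = 0.0125, so z = 2.498. The z for power is 0.842 (80%) or 1.282 (90%).
- n = 563: √(1/168.9 + 1/394.1) = 0.0920. Results: 3.340 × 0.0920 = 0.307 and 3.780 × 0.0920 = 0.348. The plan states 0.31 and 0.35, so these agree.
- n = 613: √(1/183.9 + 1/429.1) = 0.0881. Results: 0.294 and 0.333. The plan states 0.30 and 0.34. Power at those stated values is 81.8% and 91.3%, so the plan is slightly conservative here.

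The arithmetic is therefore right for four tests.

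**Step 2: family-wise error at 0.0125 when m barriers are tested, all nulls true.** The Bonferroni bound is m × 0.0125. For independent tests the error is 1 − (1 − 0.0125)^m. For equally correlated test statistics with correlation ρ it is

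1 − ∫ φ(u) [Φ((c − √ρ·u)/√(1−ρ)) − Φ((−c − √ρ·u)/√(1−ρ))]^m du, with c = 2.498.

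The documents give no correlation between these tests. I use 0 to 0.6. The upper value borrows the inter-item correlation that Section 12.1.2 assumes for three observed items, and applying it to all items is my assumption.

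| Barriers tested | Bound | Independent | Correlation 0.6 |
|---|---|---|---|
| 4 | 5.0% | 4.9% | 4.0% |
| 5 | 6.25% | 6.1% | 4.8% |
| 6 | 7.5% | 7.3% | 5.5% |
| 8 | 10.0% | 9.6% | 6.7% |

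With correlation 0.6 within each construct and none between (3 + 5 items), the figure for eight is 7.8%.

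**Step 3: cost of holding 5% with eight tests.** α = 0.05/8 = 0.00625, so z = 2.734.

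- n = 563: 3.576 × 0.0920 = 0.329 and 4.016 × 0.0920 = 0.369, against 0.307 and 0.348 for four tests. Power at the stated 0.31 and 0.35 falls from 80.9% and 90.5% to 73.8% and 85.8%.
- n = 613: 0.315 and 0.354, against 0.294 and 0.333 for four tests. Power at the stated 0.30 and 0.34 becomes 74.8% and 86.9%.

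Like for like, the loss is about 0.02 SD at either sample size.

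**The case against.** The strongest reply is that four is a planning assumption in a power section, introduced conditionally, and that the real commitment is to a 5% family-wise rate by Bonferroni. On that reading the divisor would follow the number tested. The intent is plausible, but the text says how the tests will be conducted, and the analysis section supplies no other alpha. The mismatch needs a sentence to remove it.

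Three further points stand and limit the concern.

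- **Eight is a ceiling.** Items are examined only after a latent construct is significant, with each construct tested at 0.025 and 60-65% power for small effects. Each item must then qualify. Section 12.1.2 is narrower still, since it speaks of barriers found to mediate. One of the five interactional measures, the Practitioner Orientation Scale, is a surgeon-level score from the surgeon baseline survey. The decision aid given to patients cannot change it, although it could still enter through association with engagement.
- **Correlation reduces the excess.** At 0.6 throughout, five barriers still give less than 5%.
- **The consequence is contained.** Item testing is labelled post hoc, the results mainly guide interviews, and Co-Primary Objective #1 is untouched.

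A reader might infer that the family-wise error will be about 10%, or might count nine barriers. The documents support neither. The figure near 10% needs every item to pass and the tests to be close to independent. Nine comes from Section 10.1.4.1 listing four preparatory measures where Section 12.1.1 models three. That is a separate inconsistency, and the item-level tests are defined on the modelled items.

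**Conclusion.** The concern holds in a limited form. A stated per-test alpha does not match a stated selection rule, and the desired 5% is kept only if four or fewer barriers are carried forward. Beyond four it is not guaranteed. Whether it is exceeded depends on how many pass and how correlated the tests are: it may not be at five barriers, it is at six or more over the correlation range examined, and it reaches 6.7-9.6% at the ceiling of eight. These figures assume all nulls true and a common per-test level of 0.0125. The documents do not say how many barriers are expected to pass. The plan's own power figures are sound for four tests. This should be corrected in the SAP, but it does not undermine the design.

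**What to change.** In Sections 12.1.1 and 12.1.2, replace the fixed 0.0125 with a Holm procedure at family-wise 0.05 over the barriers actually carried forward. Holm is never less powerful than Bonferroni over the same set, and it is less strict than the fixed 0.0125 when fewer than four barriers pass. Dividing by the number carried forward, or pre-specifying a rule that limits the set to four, would also close the gap. Holm over the selected set takes the selection as given. Running it over all eight items would avoid that assumption, at the eight-barrier detectable effects.

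State the detectable effects (80%/90% power) as a range for 4 to 8 barriers, on the Bonferroni level for each count: about 0.31/0.35 to 0.33/0.37 at n=563, and about 0.30/0.34 to 0.32/0.35 at n=613.

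In the same edit, reconcile two points:

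- whether only mediating barriers are tested (Section 12.1.2) or also those associated with lower engagement (Section 12.1.1);
- whether there are three preparatory items (Section 12.1.1) or four (Section 10.1.4.1).

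The cost is wording only, with no new patients or data. The stated detectable effect worsens by about 0.02 SD if all eight are tested.
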